3.4 Withdrawal and discontinuation

Patient will be withdrawn from the study if they do not pertain the enrollment criteria, or in case of absence of a Cardiac Motion monitoring procedure by the time the study ends.

Patients can withdraw their consent at any time. No additional data will be collected after patient withdrawal. As much as possible, the reason for patient withdrawal shall be collected.

In case of a patient withdrawal before any data is collected, a new enrollment may take place to ensure enough data is collected in the study.

4 STATISTICS AND METHODOLOGY

4.1. Statistical analysis plan

Sample Size. This is a feasibility study at early research stage. We plan to enroll 24 patients. We aim at a feasibility of 90% for the primary endpoint (success in 22/24 pts). With 24 patients and an expected proportion of 90%, the lower limit of the 95% confidence interval (95%CI) will be 73% (precision 17%); with an expected proportion of 95% (success in 23/24 pts), the lower limit of the 95%CI would be 79% (precision 11%).

Data Analysis. The number and proportion of success for the primary and secondary endpoint will be reported with their 95%CI. The proportion of success and 95%CI will also be reported by patients characteristics (for instance, but not limited to: age \leq / $>$ 65; BMI overweight/normo-underweight), gender, VT etiology)

Descriptive statistics (mean and standard deviation/median and quartiles or counts and percent) will be reported for the population description.

-

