2.3 Project design

This is a single center, one arm, feasibility study. The patients will undergo one Cardiac motion monitoring procedure to collect ultrasound imaging data via the Demonstrator 2 developed by EBAMed SA, Switzerland and there is no follow-up planned.

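### The planned lower limits of 73% and 79% belong to observed 22/24 (91.7%) and 23/24 (95.8%), not to 90% and 95%, so the stated precision is slightly too favourable

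*Protocol*

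**What the plan says.** Protocol section 4.1 sets the sample size ("We plan to enroll 24 patients") and the target: "We aim at a feasibility of 90% for the primary endpoint (success in 22/24 pts"). It then justifies 24 patients by precision. The first case is "With 24 patients and an expected proportion of 90%, the lower limit of the 95% confidence interval (95%CI) will be 73% (precision 17" per cent). The second is "with an expected proportion of 95% (success in 23/24 pts), the lower limit of the 95%CI would be 79% (precision 11" per cent).

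No interval method is named, and the section states no power, null rate or threshold for the lower limit. The planned analysis is descriptive: "The number and proportion of success for the primary and secondary endpoint will be reported with their 95%CI". Section 2.3 describes the design: "This is a single center, one arm, feasibility study".

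**The concern.** Each lower limit is labelled with a round percentage, and with 24 patients neither percentage can be observed: 90% of 24 is 21.6 patients and 95% is 22.8. A confidence limit depends on the count observed. If the limit was worked out at a whole count and the precision was then taken from the round percentage, the estimate and the limit in that subtraction come from different results.

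The precision statement is the only quantitative argument for 24 patients. A reader uses it to judge how much the study can say about feasibility. If the distance is understated, the design looks a little tighter than it is. The unconditional future tense in the first case adds to this, because it presents 73% as what follows from an expected 90% and not as what follows from one particular observed count.

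**Working it through.** **Inputs, all from section 4.1.** n = 24; counts 22 and 23; labels 90% and 95%; stated limits 73% and 79%; stated precision 17% and 11%. Assumption: the interval is two-sided 95%, since no method is named.

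**Step 1. Reproduce the stated limits.** The exact lower limit L for x successes solves P(X ≥ x | n = 24, p = L) = 0.025. Equivalently, it is the 2.5% quantile of a Beta(x, 25 − x) distribution.

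- x = 22: Beta(22, 3) gives L = 0.7300. Check: 276·L²²(1−L)² + 24·L²³(1−L) + L²⁴ = 0.0198 + 0.0047 + 0.0005 = 0.025.
- x = 23: Beta(23, 2) gives L = 0.7888. Check: 24·L²³(1−L) + L²⁴ = 0.0216 + 0.0034 = 0.025.

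Rounded, these are 73% and 79%, the plan's own figures. The observed proportions are 22/24 = 91.7% and 23/24 = 95.8%.

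**Step 2. Try the labels as written.** The same formula at the non-integer counts 21.6 and 22.8 is an interpolation, because neither can be observed. The other methods are there to see whether the labels can be rescued.

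| Method | at 90% | at 22/24 | at 95% | at 23/24 |
|---|---|---|---|---|
| Exact | 70.8% | 73.0% | 77.6% | 78.9% |
| Wilson | 72% | 74% | 79% | 80% |
| Agresti-Coull | 71% | 73% | 77% | 78% |
| Jeffreys | 74% | 76% | 81% | 82% |
| Wald | 78% | 81% | 86% | 88% |

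No method tried gives both 73% and 79% at exactly 90% and 95%. The exact method at the whole counts gives both. Continuity-corrected Wald and Wilson and one-sided 95% limits were also tried, and none gives the pair at the labelled percentages.

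**Step 3. Precision (estimate minus lower limit).**

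| Case | Plan | From the round label | From the observed proportion |
|---|---|---|---|
| 22/24 | 17 | 90 − 73.0 = 17.0 | 91.7 − 73.0 = 18.7 |
| 23/24 | 11 | 95 − 78.9 = 16.1 | 95.8 − 78.9 = 17.0 (16.95 before rounding) |

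The 17 combines an estimate of 90% with a limit calculated at 91.7%. Holding the estimate at exactly 90% does not rescue it: 90 − 70.8 = 19.2. The 11 does not follow even from the plan's own pair, since 95 − 79 = 16; it equals 90 − 79. That is a separate subtraction slip in the same sentence, and the same rewrite removes it.

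**Step 4. Size of the mislabelling.** 73.0 − 70.8 = 2.2 points in the first case and 78.9 − 77.6 = 1.3 points in the second, or about 1 to 2 points.

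**Context only.** At 21/24 (87.5%) the exact limit is 67.6%, so a limit of 73% needs at least 22 successes. With a true rate of 90%, P(X ≥ 22) = 276·0.9²²·0.1² + 24·0.9²³·0.1 + 0.9²⁴ = 0.272 + 0.213 + 0.080 = 0.564.

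**The case against.** The strongest reply is that nothing is hidden. The plan prints 22/24 beside its 90% aim and 23/24 beside 95%. These are the nearest whole counts to 21.6 and 22.8, and they are also the median counts at true rates of 90% and 95%, so 73% and 79% are fair central planning values. The interpolated limits describe results that cannot occur. All of this stands, and it makes the mismatch disclosed rounding. It is also fair that the 95% label depends on the method: Wilson at exactly 95% rounds to 79% too. Wilson at 90% gives 72%, however, so it does not rescue the pair.

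What the reply does not cover is the 17. Printing the count does not make 90 − 73 the distance from the estimate to its limit, because the estimate belonging to that limit is 91.7%.

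Two stronger readings are tempting. First, a reader might infer that the design fails 44% of the time, since a true rate of 90% gives at least 22/24 with probability of only 56%. The documents do not support that: they promise no power or assurance and set no rule at 73%, so the 56% contradicts no stated figure. Second, a reader might infer that 22/24 will be presented as proof of 90% feasibility. The plan does not say so. It states an aim and commits to reporting the proportion with its interval.

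**Conclusion.** The point holds as a limited error in the sample-size justification. The two limits are correct exact limits for 22/24 and 23/24 but carry the labels 90% and 95%. The first precision figure is understated as a result: 18.7 points, not 17. At 23/24 the distance is 17.0 points, against a printed 11 that is mainly the subtraction slip. The conclusion assumes a two-sided exact interval, which the plan does not name but which is the method among those tried that returns both stated limits at the stated counts. The choice of 24 patients, the endpoint and the planned analysis are unaffected.

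**What to change.** Replace the two precision statements in section 4.1 with conditional wording along these lines:

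*If 22/24 patients (91.7%) succeed, the exact (Clopper-Pearson) 95% CI lower limit is 73.0%, 18.7 points below the estimate; if 23/24 (95.8%) succeed, it is 78.9%, 17.0 points below.*

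This removes the unconditional future tense, names the method and corrects both precision figures in one edit. Adding the 21/24 case (87.5%, lower limit 67.6%) and the 56% chance of at least 22/24 at a true rate of 90% would give useful context, but it is optional and not a correction.

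The cost is one sentence in 4.1 and a stated precision that is somewhat less favourable. Keep 24 patients.

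### Protocol 4.1: the precision of 11% given for 23/24 does not follow from its own lower limit of 79%; on the definition used for 22/24 it is 16%

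*Protocol*

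**What the plan says.** Section 4.1 of the Protocol fixes the size of the study ("We plan to enroll 24 patients") and its target ("We aim at a feasibility of 90% for the primary endpoint (success in 22/24 pts"). It then describes what a 95% confidence interval would look like in two cases.

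- Expected proportion 90%, 22/24: "the lower limit of the 95% confidence interval (95%CI) will be 73% (precision 17", that is, 17%.
- Expected proportion 95%, 23/24: "with an expected proportion of 95% (success in 23/24 pts), the lower limit of the 95%CI would be 79% (precision 11", that is, 11%.

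The section defines neither precision nor the interval method. For the analysis it says: "The number and proportion of success for the primary and secondary endpoint will be reported with their 95%CI".

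**The concern.** All the figures needed for the check stand in one sentence. In the first case precision is the expected proportion minus the lower limit. In the second case that subtraction does not give the printed value, so the two precision figures cannot be compared with each other.

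The paragraph contains no hypothesis test, power calculation or minimum acceptable proportion. The expected width of the confidence interval, shown through the lower limits and the precision figures, is the whole quantitative argument for 24 patients. One of those figures is wrong, and in the favourable direction. A reader would conclude that an outcome of 23/24 pins the proportion down much more tightly than 22/24 does. Because the primary result will be reported with its 95% interval, readers can also compare the planned precision with the one obtained, and 23 successes would not deliver 11 points below the estimate.

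**Working it through.** **Inputs (all from Protocol 4.1).** n = 24. Scenario 1: expected 90%, 22/24, lower limit 73%, precision 17%. Scenario 2: expected 95%, 23/24, lower limit 79%, precision 11%. Confidence level 95%. *Assumption:* the interval is two-sided; the document does not say, but this reproduces its limits.

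**Step 1: reproduce the lower limits.** The exact (Clopper-Pearson) lower limit L solves P(X ≥ x | n, L) = 0.025, which is the 2.5% quantile of a Beta(x, n − x + 1) distribution. The upper limit is the 97.5% quantile of Beta(x + 1, n − x).

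- 22/24 = 91.7%: 73.0% to 99.0%. The stated 73% is reproduced.
- 23/24 = 95.8%: 78.9% to 99.9%. The stated 79% is reproduced. Check by hand with L = 0.7888: 24 × 0.7888^23 × 0.2112 + 0.7888^24 = 0.0216 + 0.0034 = 0.025.

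**Step 2: reproduce the first precision.** Expected minus lower limit: 90 − 73 = 17. This matches.

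**Step 3: apply the same rule to the second.** 95 − 79 = 16. The document says 11. Difference: 16 − 11 = 5 points, and 5/16 = 31%.

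**Step 4: try other meanings of precision with the exact interval.**

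| Definition | 22/24 | 23/24 | Gain |
|---|---|---|---|
| Stated in the Protocol | 17 | 11 | 6 |
| Expected proportion − lower limit | 17 | 16 | 1 |
| Observed proportion − lower limit | 18.7 | 17.0 | 1.7 |
| Half the interval width | 13.0 | 10.5 | 2.5 |

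The half-width for 23/24 would round to 11, but the first figure would then have to be 13, not 17.

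**Step 5: try other interval methods**, with expected minus lower limit for 22/24 and 23/24:

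- Wald: 9.4 and 7.2
- Wilson: 15.9 and 15.2
- Agresti-Coull: 17.0 and 16.9
- Jeffreys: 14.1 and 12.9

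None gives 17 and 11 together. One-sided 95% exact limits are 76.0% and 81.7%, so they do not reproduce the stated lower limits at all.

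**Step 6: where 11 may come from.** 90 − 79 = 11. This would fit the 90% of the first scenario having been left in the second subtraction. The document cannot show whether that happened or whether a half-width was used.

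**The case against.** The strongest counter-argument is that one reading does give both numbers. If precision means the distance of the lower limit below the 90% target, then 90 − 73 = 17 and 90 − 79 = 11. Section 4.1 does name 90% as its aim and does not define the term. The arithmetic is right, so it would be wrong to say that no rule whatever yields both figures. But that distance is not the precision of an estimate expected at 95%. It says how far the limit lies from a fixed target, not how tightly the data locate the proportion. If it was meant, the word is wrong; if it was not, the number is. The sentence needs correcting either way.

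The second counter-argument is that little depends on the 11%, and this stands. The lower limits are the more informative figures and both are correct. The 90% scenario, on which the study is planned, is consistent. No threshold or decision uses the 11%, and the planned analysis is unaffected. A careful reader can find the slip by subtraction.

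Third, the intended definition is not known, so 16% is not the only possible repair. That is also fair. However, 16% is the value that follows from the rule visible in the first half of the sentence, and it changes only one figure. The half-width reading would keep 11% but require 17% to become 13%.

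**Conclusion.** The concern holds. The 11% is inconsistent with the 95% and 79% printed beside it; on the definition that yields the 17%, the value is 16%. Precision in the more favourable scenario is overstated by 5 points, and the implied gain of 6 points between the scenarios is really 1 point. On the other two definitions applied to the exact interval the gain is 1.7 or 2.5 points, so none comes near 6.

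This rests on reading precision as expected proportion minus lower limit, which the first scenario supports, and on the two-sided exact interval, which reproduces both stated limits. The 16% itself needs only the printed figures. The error is certain but its consequence is limited: it misstates part of the sample size justification and does not invalidate the design or the choice of 24 patients.

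**What to change.** In Protocol 4.1, change the second precision figure from 11% to 16%.

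A better version would define precision, name the method (Clopper-Pearson), and give the full intervals with distances measured from the proportions actually used:

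- 22/24 = 91.7%, 95% CI 73.0% to 99.0%, lower limit 18.7 points below the estimate;
- 23/24 = 95.8%, 95% CI 78.9% to 99.9%, lower limit 17.0 points below the estimate.

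This also removes the mixing of rounded expected values (90%, 95%) with limits calculated at 91.7% and 95.8%. If half-width was intended, both figures must be restated on that basis: 13% and 11%.

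The cost is an edit to one sentence. The sample size, endpoint and analysis do not change; the stated precision becomes somewhat less favourable.

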2 PROJECT OBJECTIVES AND DESIGN

2.1 Primary objective

The primary objective of the research is to evaluate the ultrasound image quality for arrhythmia patients, to investigate potential echogenicity and artefact issues, which may arise from age, body composition, mechanical valves, leads from implanted devices, etc. in order to have a representative sample of the variety of ventricular tachycardia patients.

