2.2 Primary and additional endpoints

Objectives

The primary research objective is the proportion of subjects who have a positive evaluation in image interpretation metric and positive visual inspection of the ultrasound images.

Secondary objective; Additionally, for patients for whom a full field of view CT scan is available, the theoretical impact of probe positioning during a CT scan is analysed for hypothetical treatment planning.

Endpoints

Primary

The objective will be quantitatively assessed by scoring each patient as follows:

- A) Cardiac motion analysis performance:
 - o Score 1 if analysis of the ultrasound images with the EBAMed software gives a cardiac phase error (within R-R interval) < 0.1
 - o Score 0 otherwise
- B) Respiratory motion analysis performance:
 - o Score 1 if analysis of the ultrasound images with the EBAMed software gives a motion amplitude lower than 30 mm and if the number of breathing cycles matches the one observed from the motion of the chest.
 - o Score 0 otherwise

- C) Image quality performance:
 - o Score 1 if visual inspection by a member of San Matteo team can identify in the ultrasound images at least one of these structures: left ventricular wall, interventricular septum, or heart valve.
 - o Score 0 otherwise
- D) Image quality performance :
 - o Score 0 if visual inspection by a member of San Matteo team identifies that the heart becomes invisible for part of the time due to tissue motion linked to respiration.
 - o Score 1 otherwise

For each patient, scoring will be done for each imaging view (parasternal and apical). If the score is 2 (at least 1 point in A or B and 1 point in C or D) or higher for at least one of the imaging views, the outcome will be considered as positive. The final result will be the proportion (in %) of patients with a positive outcome defined as the number of patients with a positive evaluation divided by the total number of patients x 100.

Secondary

The objective will be quantitatively assessed by scoring each patient (only those with a CT available):

- with Score 1: if a successful radio-ablation treatment plan respecting dose constraints can be created using a clinical treatment planning software (see details below) and,
- with Score 0: if it is not possible to create such a treatment plan .

The final result will be the proportion of patients (in %) with a 1 Score: number of patients with score 1 divided by the number of patients with Score 0 or 1 x 100.

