3.1.1 Demographics and cardiovascular history

The patient will be asked to confirm his/her demographics and cardiovascular history.

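### Section 2.1 asks what spoils the images, but section 4.1 breaks down by patient characteristics only a best-of-two-views composite with about 2 expected failures, which can miss a factor that spoils one view

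*Protocol*

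**What the plan says.** Section 2.1 (Primary objective) sets out to evaluate ultrasound image quality and "to investigate potential echogenicity and artefact issues, which may arise from age, body composition, mechanical valves, leads from implanted devices".

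Section 2.2 scores four items (A cardiac motion, B respiratory motion, C structure visible, D heart not lost to view with respiration) in each of the apical and parasternal views. These become one result per patient. A view passes when it has a point from the A/B pair and a point from the C/D pair, and a single passing view suffices: "for at least one of the imaging views, the outcome will be considered as positive". What is reported from this is one patient-level figure: "The final result will be the proportion (in %) of patients with a positive outcome".

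Section 4.1 plans 24 patients and aims for success in 22. It reports the proportion of success for the primary and secondary endpoints with 95% confidence intervals, and adds: "The proportion of success and 95%CI will also be reported by patients characteristics". The examples given are age, BMI, gender and VT etiology, in a list expressly left open. No breakdown by view or by item is stated.

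Section 3.1 says that patients with cardiac or non-cardiac thoracic implants are of interest.

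**The concern.** The question in section 2.1 is which patient features degrade the images. Answering it needs an outcome that moves when an image is degraded. The composite is built to ask something else: whether at least one usable view can be obtained. It forgives the complete loss of one view and partial loss in the other. It also lets D make up for C, so a view in which none of the listed structures is identified can still pass if A or B scores 1.

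If device leads spoiled the apical view in every carrier while the parasternal view stayed usable, the planned breakdown would show carriers succeeding. A reader of the report could take that as evidence that leads cause no problem, although the scores already collected would show the opposite.

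**Working it through.** **Inputs.** From section 4.1: n = 24; planned success 22/24, alternative 23/24. From section 2.2: 4 items, 2 views, and the composite rule. The protocol gives no subgroup sizes, so those below are assumptions.

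**1. The plan's own figures.** The exact (Clopper-Pearson) lower 95% limit for x successes in n is the 2.5% quantile of Beta(x, n − x + 1).
- 22/24: 73.0% (stated 73%).
- 23/24: 78.9% (stated 79%).

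Both stated lower limits reproduce.

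**2. What a positive patient can hide.** One passing view needs one point from A/B and one from C/D, so 2 points. Items per patient: 4 × 2 = 8. Items that can be 0 in a positive patient: 8 − 2 = 6. Over the study, 24 × 8 = 192 scores are reduced to 24 yes/no results.

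**3. Failures available.** 24 − 22 = 2, or 24 − 23 = 1 under the alternative.

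**4. What 2 failures can show.** If both fall in a subgroup of k patients, the probability under no association is k(k − 1)/(24 × 23) = k(k − 1)/552. This is the two-sided Fisher p for k below 12. At k = 12 the mirror-image split is equally likely, so it doubles.

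| k | calculation | two-sided p |
|---|---|---|
| 12 | 2 × 132/552 | 0.478 |
| 8 | 56/552 | 0.101 |
| 6 | 30/552 | 0.054 |
| 5 | 20/552 | 0.036 |
| 4 | 12/552 | 0.022 |

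The protocol plans no such test; the values only gauge how much information 2 failures carry. In the descriptive terms it does plan, a 12/12 split with both failures on one side gives exact intervals of 51.6% to 97.9% (10/12) and 73.5% to 100% (12/12), which overlap widely.

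**5. A constructed example, consistent with 22/24.** Suppose 8 patients carry leads, all 8 fail the apical view and pass the parasternal view, and the 2 patients who fail both views are non-carriers. The other 14 non-carriers pass both views.
- Composite: carriers 8/8 = 100% (exact interval 63.1% to 100%); non-carriers 14/16 = 87.5%.
- Apical view alone: carriers 0/8; non-carriers 14/16.

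The composite points the wrong way; the per-view table shows the problem at once. This shows what is possible, not what is likely.

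**6. How much more the per-view scores might carry.** If the views failed independently at equal rates, the per-view failure rate would be √(2/24) = 28.9%, and 0.289 × 24 ≈ 7 failures per view. If they failed in exactly the same patients, it would be 2 per view, with no gain from counting views separately. Under these two assumptions the range is 2 to 7, against 2 in the composite.

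**The case against.** The strongest reply is that descriptive tables by item and view are ordinary SAP content, and that section 4.1 forbids nothing. Section 2.2 also restates the primary objective as the proportion of positive patients, which the plan does estimate. Section 2.1's sentence ends by referring to a representative sample, so its factors can partly be read as describing the patients wanted. The best-of-two rule has a purpose too: section 2.2 places the virtual probe for treatment planning according to the better view.

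Much of this stands. The composite is a reasonable primary proportion, and the tables may be added elsewhere. What remains is that section 4.1 does state which outcome is broken down by characteristics, and that outcome is insensitive to the investigation named in section 2.1. Adding factors to the open list would not cure this.

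A reader might infer more than the text supports:
- *That the composite is the only outcome broken down.* The preceding sentence in section 4.1 covers both endpoints, so the treatment-plan endpoint may be included. The composite is the only image-quality outcome broken down.
- *That valves and leads are excluded or not recorded.* The list is open, and age and body composition (as BMI) are named. Section 3.1.1 says "The patient will be asked to confirm his/her demographics and cardiovascular history", which may well cover valves and leads. Section 2.2 gives demographics and cardiovascular history only as examples of the influential data to be collected. The CRF is not shown.
- *That losing one point in both views never matters.* It is harmless only where at least one view still keeps a point in A/B and one in C/D.
- *That all subgroups would look alike.* With 2 failures, 10/12 against 12/12 is 83% against 100%; the difference is visible but very imprecise.

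**Conclusion.** The concern holds as a mismatch between objective and analysis. The image-quality outcome broken down by characteristics tolerates 0 on 6 of 8 items and leaves 2 failures at the planned rate (1 at 23/24), so it can miss a factor that systematically spoils one view. The failure counts rest on the protocol's own target; subgroup sizes, and the 2 to 7 failures per view, are assumptions.

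It would go too far to say that the primary objective is unanswerable or that the 90% target is undermined. The primary proportion as defined in section 2.2 is unaffected. What is at risk is the part of section 2.1 about the sources of poor images, which could be left open or wrongly reported as showing no problem.

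**What to change.** In section 4.1:
- Keep the composite as the primary proportion.
- For the section 2.1 objective, add a tabulation of scores A, B, C and D separately for the apical and parasternal views, by patient characteristic, descriptively and without formal tests.
- Name mechanical valve, device leads and other thoracic implant (each yes/no) among the characteristics, and confirm that the CRF records them.
- State that conclusions about echogenicity and artefacts rest on these per-view scores.

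Section 2.2 already requires scoring in each view, so no new procedure or patients are needed: only analysis wording and, if not already present, three CRF items. The price is more tables with small counts. The 192 scores are correlated measurements on 24 patients, not a larger sample. Parasternal recordings also vary under the procedure in section 3.1.2 (probe fixed or hand-held, breath-holds optional when hand-held), so the tables for that view should show the acquisition mode and be read with it in mind.

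### The by-characteristic tables use a composite yes/no success with only about two expected failures, so they can say almost nothing about how age and body composition affect the images

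*Protocol*

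**What the plan says.** Section 2.1 of the protocol sets out to investigate "potential echogenicity and artefact issues, which may arise from age, body composition", together with mechanical valves and device leads.

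Section 2.2 scores each patient in each of two views. Score A is 1 if the software "gives a cardiac phase error (within R-R interval) < 0.1". Score B concerns respiratory motion. Scores C and D are visual yes/no readings. A patient is positive if at least one view has a point from A or B and a point from C or D.

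Section 4.1 covers sample size and analysis: "We plan to enroll 24 patients" and "We aim at a feasibility of 90% for the primary endpoint (success in 22/24 pts"), with an alternative scenario "with an expected proportion of 95% (success in 23/24 pts"). On characteristics it says: "The proportion of success and 95%CI will also be reported by patients characteristics". The examples are age split at 65, "BMI overweight/normo-underweight", gender and VT etiology. The list is expressly open. The method, a proportion of successes with its interval within categories, is the only one named. Means, medians and quartiles are planned for describing the population, not for the software's measurements.

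**The concern.** Phase error is compared with a numerical limit, so it must be measured before score A can be assigned. Age and BMI are also measured quantities. The plan reduces the error to pass/fail, merges it with three other scores over two views, and sets the result against characteristics that have themselves been split in two. Errors of 0.01 and 0.09 count as equal, while 0.09 and 0.11 count as opposites.

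With success expected in 90% or more of patients, very few failures remain to be distributed over categories. The better the system performs, the less these tables can say about what makes the images worse. The part of the primary objective that concerns age and body composition would then go largely unanswered, although measurements that bear on it are needed anyway for scoring.

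**Working it through.** **Inputs.** From section 4.1: N = 24; planned success 22/24 (stated as 90%) or 23/24 (stated as 95%); 95% intervals, taken as two-sided; age and BMI split in two. From section 2.2: the 0.1 limit and the composite rule. Not in the protocol, hence assumed: the distribution of phase error, the share of patients below 0.1, the shares over 65 or overweight, and the strength of any relation.

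**1. The plan's own figure.** The protocol states that "the lower limit of the 95% confidence interval (95%CI) will be 73% (precision 17"%). Exact (Clopper-Pearson) limits give 73.0% for 22/24 and 78.9% for 23/24. Both stated lower limits (73% and 79%) reproduce, so the same interval method is used below.

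**2. What the tables can show at 22/24.** Take an even split and the most extreme case, both failures in one group:
- 10/12: 95% CI 52 to 98%
- 12/12: 95% CI 74 to 100%
- Fisher p = 2 × C(12,2)/C(24,2) = 2 × 66/276 = 0.48

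More failures, all on one side of 12/12:
- four: 2 × 495/10,626 = 0.093
- five: 2 × 792/42,504 = 0.037

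So an even split needs at least five failures, all on one side, for p < 0.05. With two failures, both would have to fall in a group of five patients or fewer: C(5,2)/276 = 10/276 = 0.036, against C(6,2)/276 = 15/276 = 0.054 for a group of six. At 23/24 there is one failure; in an even split this gives 11/12 (62 to 100%) against 12/12, p = 1.0. Nothing in this step depends on a distributional assumption.

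**3. Information kept, for phase error against age or BMI only.** Cutting a normal variable at proportion p keeps φ(z_p)²/[p(1−p)] of the information on a weak linear association. When both variables are cut, the factors multiply.
- Outcome, 90% passing: 0.342
- Age or BMI, median split: 0.637
- Product: 0.342 × 0.637 = 0.218, and 24 × 0.218 = 5.2 patients

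| Success | 50/50 split | 80/20 split |
|---|---|---|
| 90% | 5.2 | 4.0 |
| 22/24 | 4.7 | 3.6 |
| 95% | 3.4 | 2.6 |
| 23/24 | 3.0 | 2.3 |

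If far fewer passed, less would be lost: with median splits, 7.5 patients at 80%, 8.8 at 70% and 9.7 at 50%. The product rule is for weak association. The exact 2×2 correlation at 90% with a median split gives 5.2, 5.1, 4.9 and 4.3 patients at true correlations of 0.1, 0.3, 0.5 and 0.7.

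For a characteristic that is binary by nature, only the outcome cut costs information: 24 × 0.342 = 8.2 patients at 90%.

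**4. Role of the composite.** The 90% belongs to the composite, not to score A. With normal phase error, no yes/no outcome with 90% success can keep more than 0.342 of the phase-error information, and a cut on the error itself is the case that reaches it. At that success rate 5.2 is therefore a ceiling for the phase-error relation.

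**The case against.** The strongest case on the other side has five parts.

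- **The outcome tabulated is not phase error cut at 0.1.** It is the composite, and a patient with an error of 0.1 or more can still be positive through score B or the other view. This stands. A reader might infer that the plan relates score A directly to age and BMI, or that 90% is the expected pass rate for score A. The protocol says neither.
- **The information loss is not general.** A reader might infer that the 24 patients carry only about five patients' worth of information on everything that degrades the images. They do not. Scores C and D, which the protocol labels image quality, are yes/no readings with no measured version described; gender, etiology, valves and leads are categorical. This stands and limits step 3 to phase error against age and BMI.
- **No test is planned.** Section 4.1 promises proportions and intervals only. A reader might infer an underpowered planned comparison; there is none. The Fisher values above only gauge how little the tables can separate. The wide, overlapping intervals lead to the same conclusion.
- **The objective may be about coverage.** Its sentence ends with obtaining a representative sample, the endpoint is one proportion, and the study is an early feasibility study. This is a fair reading of emphasis, but the sentence does name age and body composition as sources of problems to be investigated, and the tables are the only analysis offered for that.
- **Exploratory detail can be left to a separate analysis plan.** True in general. Here, however, the protocol has already fixed the form of the outcome and given example cuts. The point concerns that stated choice, and the open list of characteristics does not open the method.

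One practical reservation also stands. The protocol does not say that there is one usable error per view. Recordings include free breathing and breath-holds, and the parasternal probe may be hand-held for as little as one minute. Any added analysis must say which sequence it uses and how unusable recordings count.

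**Conclusion.** The concern holds in a limited form. The described tables of composite success by characteristic can show almost nothing about age or body composition at the planned success rates. That follows from the counts alone.

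The figure of about 2 to 5 of 24 patients is conditional. It applies to phase error against age or BMI, with approximate normality, weak to moderate linear association, 90% to 96% success and splits between 50/50 and 80/20. It rises to about 10 if only half the patients pass. For binary characteristics the equivalent is about 8 at 90%, and for scores C and D no such loss can be claimed.

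The primary proportion and its interval are not affected.

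**What to change.** Keep the composite, the 0.1 limit, the primary proportion and the planned tables. In section 4.1 add an exploratory analysis, separately for the apical and parasternal views:

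- the median and quartiles of phase error;
- its relation to age and to BMI as continuous variables, by Spearman correlation with 95% CI;
- one named acquisition sequence as the source of the value, for example free breathing, which is acquired in both views;
- the number of recordings with no usable phase error, with these ranked as worst.

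The cost is a few lines of text and a little more analysis. The error is already needed for score A, and demographics are already collected, so no patient, procedure or visit is added. The results are exploratory only, and parasternal recordings made with a fixed and with a hand-held probe may not be comparable, which should be stated when they are reported.
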